## **Safety measures**

- Close monitoring of adverse events, safety lab, ECG and vital signs
- To reduce the risk of cardiovascular events, subjects with additional risk factors (smoking, adipositas, hypertension) are not to be entered in the trial, per inclusion/exclusion criteria and study restrictions.
- Thrombophilic testing will be performed on each subject to detect a potential thrombophilic disposition (deficiency of antithrombin III, resistance to activated protein C, etc.).
- In addition to the general inclusion examination, the suitability of subjects for taking this oral contraceptive will be assessed by a gynaecologist prior to trial entry.
- Although rare, a potential for drug-induced liver injury is under constant surveillance by sponsors and regulators. Therefore, this study requires timely detection, evaluation, and follow-up of alterations in selected liver laboratory parameters to ensure subjects' safety.

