#### **3.1.1 Administrative structure of the trial**

The trial will be conducted at the  
under the supervision of the Principal Investigator.

Proprietary confidential information © 2017 Boehringer Ingelheim International GmbH or one or more of its affiliated companies

The trial medication will be provided by the Clinical Trial Supplies Unit (CTSU), BI Pharma GmbH & Co. KG, Biberach, Germany.

On-site monitoring will be performed by BI or a contract research organisation appointed by BI.

The analyses of BI 409306 concentrations in plasma will be performed at the Department of Drug Metabolism and Pharmacokinetics, BI Pharma GmbH & Co. KG, Biberach, Germany.

The analyses of ethinylestradiol and levonorgestrel concentrations in plasma will be performed at the laboratory of

Genotyping of cytochrome P450 (CYP) isoenzyme 2C19 will be performed at the study site.

Safety laboratory tests will be performed by the local laboratory of the trial site.

Electrocardiograms (ECG) are to be evaluated for subject safety at the study site by the investigator or representative.

Data management and statistical evaluation will be done by BI according to BI SOPs.

The trial is sponsored by Boehringer Ingelheim Pharma GmbH & Co. KG, Germany.

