20. Subject is assessed as unsuitable for inclusion by the investigator, for instance, because considered not able to understand and comply with study requirements, or has a condition that would not allow safe participation in the study.
21. Any relevant finding of the gynaecological examination
22. Thrombotic predisposition according to thrombophilic testing
23. Existing or history of arterial thrombotic or embolic processes, conditions which predispose to them e.g. disorders of the clotting processes, valvular heart disease and atrial fibrillation
24. Existing or history of confirmed venous thromboembolism, family history of venous thromboembolism, and other known risk factors for venous thromboembolism.
25. Relevant varicosis
26. Use of hormone-containing intrauterine device, depot injection or contraceptive implants

For study restrictions, refer to [Section 4.2.2](#).

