### **5.2.3 Assessment of safety laboratory parameters**

For the assessment of laboratory parameters, blood and urine samples will be collected by the trial site at the time points indicated in the [Flow Chart](#) after the subjects have fasted for at least 10 h. Overnight fasting is not required at the discretion of the investigator or designate for retests.

The parameters that will be determined are listed in [Tables 5.2.3: 1](#) and [5.2.3: 2](#). Reference ranges will be provided in the ISF.

Manual differential white blood cell count or urine sediment examinations will only be performed if there is a clinically relevant abnormality in the automatic blood cell count or in the urinalysis, respectively.

Proprietary confidential information © 2017 Boehringer Ingelheim International GmbH or one or more of its affiliated companies

**Table 5.2.3: 1** Routine laboratory tests

Functional lab group	Test name	Set A 	Set B 	Set C 
Hematology	Hematocrit	x	x	x
	Hemoglobin	x	x	x
	Red blood cell count (RBC)	x	x	x
	Reticulocyte count	x	-	-
	White blood cell count (WBC)	x	x	x
	Platelet count	x	x	x
Automatic WBC differential (relative)	Neutrophils, eosinophils, basophils, monocytes, lymphocytes	x	x	x
Manual differential WBC (if automatic differential WBC is clinically relevant abnormal)	Polymorphnuclear neutrophils (segs), band neutrophils (stabs), eosinophils, basophils, monocytes, lymphocytes	x	x	x
Coagulation	Activated partial thromboplastin time (aPTT)	x	-	x
	Prothrombin time (Quick's test and INR)	x	-	x
	Thrombophilic tests 	x	-	-
Enzymes	Aspartate transaminase (AST/GOT)	x	x	x
	Alanine transaminase (ALT/GPT)	x	x	x
	Alkaline phosphatase (ALP)	x	x	x
	Gamma-glutamyl transferase (GGT)	x	x	x
	Creatine kinase (CK)	x	x	x
	CK-MB, only if CK is elevated	x	x	x
	Lactate dehydrogenase (LDH)	x	x	x
	Amylase	x	-	-
	Lipase	x	-	-
Hormones	Thyroid stimulating hormone (TSH)	x	-	-
Substrates	Serum Glucose	x	x	x
	Creatinine	x	x	x
	Total bilirubin	x	x	x
	Direct bilirubin	x	x	x
	Total protein	x	-	-
	Uric acid	x	-	-
	Total cholesterol	x	-	-
	Triglycerides	x	-	-
	hs-CRP (high sensitivity C-Reactive Protein)	x	x	x

 Parameters of Set A will be determined at the screening examination

 Parameters of Set B will be determined during treatment periods at the time points given in the [Flow Chart](#)

 Parameters of Set C will be determined at the end of trial examination

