 Thrombosis panel (Lupus anticoagulant / Anti-cardiolipin antibody (ACA) (IgM, IgG) / Protein C / Protein S / antithrombin III /anti-beta2 Glycoprotein I antibody (IgM, IgG) / Plasminogen)

Proprietary confidential information © 2017 Boehringer Ingelheim International GmbH or one or more of its affiliated companies

**Table 5.2.3: 1** Routine laboratory tests (cont.).

Functional lab group	Test name	Set A 	Set B 	Set C 
Electrolytes	Sodium	x	x	x
	Potassium	x	x	x
	Calcium	x	-	-
Urinalysis  (Stix)	Urine nitrite		x	x
	Urine protein (albumin)			
	Urine glucose			
	Urine ketone			
	Urobilinogen			
	Urine bilirubin			
	Urine erythrocytes (RBC)			
	Urine leukocytes (WBC)			
	Urine pH			

 Parameters of Set A will be determined at the screening examination

 Parameters of Set B will be determined during treatment periods at the time points given in the [Flow Chart](#)

 Parameters of Set C will be determined at the end of trial examination

 Urine sediment: Microscopic examination if erythrocytes, leukocytes nitrite or protein are abnormal in urine. Only positive findings will be reported (for instance, the presence of sediment bacteria, casts in sediment, squamous epithelial cells, erythrocytes, leukocytes)

The tests listed in Table 5.2.3: 2 are exclusionary laboratory tests which may be repeated as required. The results will not be entered in the CRF/database and will not be reported in the CTR.

**Table 5.2.3: 2** Exclusionary laboratory tests

Functional lab group	Test name	Set A 	Set B 	Set C 
Drug screening (urine)	Includes: Amphetamine/MDA Barbiturates Benzodiazepine Cannabis, Cocaine Methadone Methamphetamines/MDMA/XTC Opiates , Phencyclidine Tricyclic antidepressants	x	-	-
Infectious serology (blood)	Includes: Hepatitis B surface antigen (qualitative) Hepatitis B core antibody (qualitative) Hepatitis C antibodies (qualitative) HIV 1+2-antibody	x	-	-
Pregnancy test (urine)	Beta human chorionic gonadotropin (beta-HCG)	x	x	x

 Parameters of Set A will be determined at the screening examination

 Parameters of Set B will be determined during treatment periods at the time points given in the Flow Chart

 Parameters of Set C will be determined at the end of trial examination

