### **6.2 DETAILS OF TRIAL PROCEDURES AT SELECTED VISITS**

#### **6.2.1 Screening and run-in period**

After having been informed about the trial, all subjects will give their written informed consent in accordance with GCP and local legislation prior to enrolment in the study.

For information regarding laboratory tests (including drug and virus screening), ECG, vital signs, physical examination gynaecological examination including Pap smear, refer to [Sections 5.2.3](#) to [5.2.5](#).

Pharmacogenomic genotyping will be performed in those subjects whose genotypes are not known (for details see [Section 5.3](#)).

Proprietary confidential information © 2017 Boehringer Ingelheim International GmbH or one or more of its affiliated companies

After passing the screening examination the subjects will be allocated to a subject number and will be given a 2-month package of Microgynon® tablets for the run-in-period. The intake of these tablets starts depending on the subjects' actual menstruation cycle and at least 28 days before Day 1 of the treatment period (see [Section 3.1](#)). In the last 7 days of the run-in period, no Microgynon® tablets will be taken to induce a withdrawal bleeding.

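### The screening thrombosis panel lists no assay for resistance to activated protein C, a condition that Safety measures says thrombophilic testing is meant to detect

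*Protocol*

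**What the plan says.** The protocol touches on thrombophilia screening in four places.

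- **Safety measures** commits to testing every subject and names two conditions as examples: "Thrombophilic testing will be performed on each subject to detect a potential thrombophilic disposition (deficiency of antithrombin III, resistance to activated protein C, etc". It names conditions, not assays.
- **Section 6.2.1** directs the site to the laboratory section for screening tests, in the sentence that begins "For information regarding laboratory tests (including drug and virus screening". **Section 5.2.3** then fixes the scope: "The parameters that will be determined are listed in" Tables 5.2.3: 1 and 5.2.3: 2.
- **Table 5.2.3: 1** has a coagulation row for thrombophilic tests, marked for Set A (screening) only. Its footnote 4 gives the content: "Thrombosis panel (Lupus anticoagulant / Anti-cardiolipin antibody (ACA) (IgM, IgG) / Protein C / Protein S / antithrombin III", followed by "anti-beta2 Glycoprotein I antibody (IgM, IgG) / Plasminogen". The list closes there, with no wording to suggest that it is illustrative.
- **Section 3.3.3**, exclusion 22, removes a subject for "Thrombotic predisposition according to thrombophilic testing".

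The SAP does not deal with thrombophilia testing.

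**The concern.** Safety measures tells an ethics committee or investigator that screening is meant to pick up resistance to activated protein C. The section that tells the site which tests to run includes nothing that would do so. Section 1.2.2 states that combined contraceptives, Microgynon included, should not be used in women with or at risk of venous thromboembolism (VTE). The first 21 to 42 days of tablets are taken at home, so screening is the point at which an unrecognised predisposition would have to be found. At stake are the delivery of one stated safeguard and the accuracy of the benefit-risk text.

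**Working it through.** The protocol gives no figure for this point, so the check is a comparison of texts. Each test listed for screening that bears on clotting is set against the two conditions that Safety measures names.

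| Listed for screening (Set A) | Antithrombin III deficiency | Resistance to activated protein C |
|---|---|---|
| Lupus anticoagulant | no | no |
| Anti-cardiolipin antibody | no | no |
| Protein C | no | no |
| Protein S | no | no |
| Antithrombin III | yes | no |
| Anti-beta2 glycoprotein I antibody | no | no |
| Plasminogen | no | no |
| aPTT | no | no |
| Prothrombin time | no | no |

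1. **Panel.** Footnote 4 has seven items. One matches antithrombin III deficiency and none is an assay for resistance to activated protein C. The protein C entry concerns the protein itself, whereas resistance is a poor response to its activated form. That distinction is general laboratory knowledge. The protocol gives no assay methods, so this is an assumption of the check.
2. **Rest of the laboratory section.** The only other coagulation rows are aPTT and prothrombin time, which are routine clotting times. Table 5.2.3: 2 covers drug screening, infectious serology and pregnancy.
3. **Genotyping.** Section 3.1.1 says "Genotyping of cytochrome P450 (CYP) isoenzyme 2C19 will be performed at the study site", and footnote 1 of the Flow Chart gives the same purpose for the pharmacogenetic sample. Part of section 5.3 is absent from the public text, so this step is less complete than the panel comparison, which does not depend on it.
4. **Timing.** The thrombophilic tests are in Set A only, so no later visit offers a second chance.
5. **Currency.** Footnote 4 is complete in the public text. Amendment 1 revised this panel, and the current version still has no such assay.
6. **Other criteria.** Exclusion 23 reaches "conditions which predispose to them e.g. disorders of the clotting processes", and exclusion 24 reaches personal history, family history and other known risk factors for VTE. Both act on what is already known about the woman.

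**Scale, for context only.** The section on Microgynon risks gives about 20 VTE per 100,000 women per year on this class of pill. There is no Day 0.

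- Shortest span from first to last tablet, tablet-free week included: Days -28 to -1 (28) plus Days 1 to 21 (21) = 49 days.
- Longest span: Days -49 to -1 (49) plus 21 = 70 days.
- Expected events in 16 women, shortest: 16 × 49/365.25 = 2.15 woman-years; × 0.0002 = 0.0004.
- Expected events in 16 women, longest: 16 × 70/365.25 = 3.07 woman-years; × 0.0002 = 0.0006.

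These are VTE of any cause at a general rate. They do not estimate what the missing assay would prevent.

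**The case against.** The strongest reply is that the two texts do not truly conflict. Safety measures is itself current protocol text that promises testing, the laboratory table does not forbid further tests, and exclusion 22 is not tied to footnote 4. A site that read Safety measures and added the assay could apply exclusion 22 to the result. All of that stands. A reader might infer that exclusion 22 is incapable of catching such a case, and the documents do not support that. What remains is that the section that instructs the laboratory does not call for the assay, so a site working from the table alone would not run it.

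It can also be said that the phrase is only an example in an open-ended list. The open ending allows for further conditions, but it does not withdraw one that is named.

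A reader might also infer that laboratory screening is the sole protection for a woman without a personal history. That goes too far. A gynaecologist assesses each subject's suitability for the pill before entry. Smoking, obesity and hypertension are excluded as added risk factors. Exclusion 24 includes family history, exclusion 25 covers relevant varicosis, and exclusion 20 leaves room for the investigator's judgement. None of these detects the trait itself, but several lower the risk.

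Finally, the VTE figures might be taken as the size of the defect. They are not: the documents give neither a prevalence nor a relative risk for this condition.

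**Conclusion.** The mismatch holds. Of the two conditions that Safety measures names, antithrombin III deficiency has a listed test and resistance to activated protein C has none. A site following the laboratory table exactly would not detect a previously unknown case, and exclusion 22 would have no listed result to act on for that condition.

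Severity is minor. Expected VTE of any cause in the whole trial is well below one in a thousand at the protocol's own rate, and the share that the missing assay could affect cannot be quantified from the documents. No pharmacokinetic endpoint, sample size consideration or SAP analysis is touched. The conclusion rests on reading section 5.2.3 as the operative instruction, and on the ordinary laboratory meaning of the listed tests.

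**What to change.** Add an activated protein C resistance assay to footnote 4 of Table 5.2.3: 1, in Set A at screening only. The cost is one more assay per screened subject, at a visit that already includes coagulation tests, and possibly a few more screen failures.

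Leave exclusion 22 worded as it is. Tying it to footnote 4 would narrow it, because a positive result from an unlisted thrombophilia test would then fall outside it.

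If the clinical team judges the assay unnecessary, delete resistance to activated protein C from Safety measures, so that the benefit-risk text does not claim it. That has no operational cost, but it only aligns the wording and adds no protection.

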### **3. DESCRIPTION OF DESIGN AND TRIAL POPULATION**

#### **3.1 OVERALL TRIAL DESIGN AND PLAN**

The study will be performed as an open-label, run-in period, two treatment periods in a fixed-sequence.

A total of 16 healthy Korean premenopausal female volunteers with CYP2C19 PM genotype will participate in the trial.

##### **Run-in-period**

All subjects will undergo a run-in period (Visit 2) that starts between Day -49 and Day -28. In this period, the subjects will take one tablet of Microgynon® daily (for 21-42 days) until Day -8. In the last 7 days of the run-in period (Day -7 to Day -1) no treatment will be given in order to induce withdrawal bleeding. The next day will be Day 1. Subjects who have already been using oral contraceptives before the study will start the run-in period after the usual tablet-free interval of 7 days. Subjects who have been using hormonal contraceptive vaginal rings before the study will start the run-in-period after the usual hormone-free interval of 7 days.

##### **Treatment period**

Visit 3 follows directly after the run-in-period. Subjects will be treated as below.

1 tablet of Microgynon® QD with 240 mL water on Days 1 to 17 (R2 on Day 17)  
1 tablet of BI 409306 and 1 tablet of Microgynon® with 240 mL water on Day 18 (T1 and T2)  
1 tablet of Microgynon® QD with 240 mL water on Days 19 to 21  
1 tablet of BI 409306 with 240 mL water on Day 29 (R1)

Period	Screening	Run-in	Treatment						End of Trial
Visit	1	2	3						4
Day	-70 to -29	-49 to -1	1 to 16	17	18	19 to 21	...	29	33 to 35
BI 409306					X			X	
Microgynon®		X*	X	X	X	X			

\* depending on the subjects' actual menstruation cycle. No Microgynon® on the Days -7 to -1.

An overview of all relevant trial activities is provided in the [Flow Chart](#). For visit schedule and details of trial procedures at selected visits, refer to [Sections 6.1](#) and [6.2](#), respectively.

#### **3.1.1 Administrative structure of the trial**

The trial will be conducted at the  
under the supervision of the Principal Investigator.

Proprietary confidential information © 2017 Boehringer Ingelheim International GmbH or one or more of its affiliated companies

The trial medication will be provided by the Clinical Trial Supplies Unit (CTSU), BI Pharma GmbH & Co. KG, Biberach, Germany.

On-site monitoring will be performed by BI or a contract research organisation appointed by BI.

The analyses of BI 409306 concentrations in plasma will be performed at the Department of Drug Metabolism and Pharmacokinetics, BI Pharma GmbH & Co. KG, Biberach, Germany.

The analyses of ethinylestradiol and levonorgestrel concentrations in plasma will be performed at the laboratory of

Genotyping of cytochrome P450 (CYP) isoenzyme 2C19 will be performed at the study site.

Safety laboratory tests will be performed by the local laboratory of the trial site.

Electrocardiograms (ECG) are to be evaluated for subject safety at the study site by the investigator or representative.

Data management and statistical evaluation will be done by BI according to BI SOPs.

The trial is sponsored by Boehringer Ingelheim Pharma GmbH & Co. KG, Germany.

### **3.2 DISCUSSION OF TRIAL DESIGN, INCLUDING THE CHOICE OF CONTROL GROUP(S)**

The trial will be conducted as an open-label, two-period, fixed-sequence trial.

The design of the study allows each subject to serve as her own control. The comparison between treatments is based on a comparison within subjects rather than between subjects. This means that the inter-subject variability is removed from the comparison between treatments [\[R94-1529\]](#).

Considering possible variations of enzyme activities during the menstrual cycle [\[R09-5728\]](#), a fixed-sequence design was chosen to ensure that pharmacokinetic parameters of the respective investigational drugs would be determined in all subjects at the same time point of the menstrual cycle. To exclude possible interaction with any preceding oral contraceptive regime and to minimize the influence of adaptation to a newly administered oral contraceptive, all participants will undergo a run-in period of at least 28 days (including treatment with Microgynon® for at least 21 days) before the beginning of the first study period. The duration of Microgynon® intake was chosen to ensure steady state condition for Microgynon®. The study design is considered appropriate to assess a possible influence of BI 409306 on the steady state pharmacokinetics of ethinylestradiol and levonorgestrel.

### **3.3 SELECTION OF TRIAL POPULATION**

It is planned that 16 healthy Korean premenopausal female subjects with CYP2C19 poor metabolizer (PM) genotype will enter the study. The CYP2C19 PM genotype is defined by

Proprietary confidential information © 2017 Boehringer Ingelheim International GmbH or one or more of its affiliated companies

the carriage of two non-functional alleles (\*2 and \*3) of the CYP2C19 gene. Subjects will be recruited from the volunteers' pool of the trial site.

A log of all subjects enrolled into the study (i.e. having given informed consent) will be maintained in the ISF at the investigational site irrespective of whether they have been treated with investigational drug or not.

### **3.3.1 Main diagnosis for study entry**

The study will be performed in healthy female subjects.

### **3.3.2 Inclusion criteria**

Subjects will only be included into the trial, if they meet the following criteria:

1. Healthy CYP2C19 PM genotyped (defined [5.3.1](#)) premenopausal female subjects according to the investigator's assessment, based on a complete medical history including a physical examination, vital signs (BP, PR), 12-lead ECG, and clinical laboratory tests.
2. Korean ethnicity according to the following criteria ; be a current Korean passport or national identification card holder, and have parents and grandparents who were all born in Korea
3. Age of 19 to 40 years (incl.)
4. BMI of 18.5 to 25.0 kg/m^2 (incl.)
5. Signed and dated written informed consent prior to admission to the study in accordance with GCP and local legislation
6. Female subjects who meet any of the following criteria starting from at least 30 days before the first administration of trial medication and until 30 days after trial completion:
  - Use of adequate contraception, e.g. non-hormonal intrauterine device *plus* condom
  - Sexually abstinent
  - A vasectomised sexual partner (vasectomy at least 1 year prior to enrolment)
  - Surgically sterilised (including hysterectomy)

### **3.3.3 Exclusion criteria**

1. Any finding in the medical examination (including BP, PR or ECG) is deviating from normal and judged as clinically relevant by the investigator
2. Repeated measurement of systolic blood pressure outside the range of 90 to 140 mmHg, diastolic blood pressure outside the range of 50 to 90 mmHg, or pulse rate outside the range of 45 to 90 bpm
3. Any laboratory value outside the reference range that the investigator considers to be of clinical relevance
4. Any evidence of a concomitant disease judged as clinically relevant by the investigator

Proprietary confidential information © 2017 Boehringer Ingelheim International GmbH or one or more of its affiliated companies

5. Gastrointestinal, hepatic, renal, respiratory, cardiovascular, metabolic, immunological, oncologic or hormonal disorders
6. Cholecystectomy and/or surgery of the gastrointestinal tract that could interfere with the pharmacokinetics of the trial medication (except appendectomy and simple hernia repair)
7. Diseases of the central nervous system (including but not limited to any kind of seizures or stroke), and other relevant neurological or psychiatric disorders
8. History of relevant orthostatic hypotension, fainting spells, or blackouts
9. Chronic or relevant acute infections
10. History of relevant allergy or hypersensitivity (including allergy to the trial medication or its excipients)
11. Use of drugs within 30 days prior to administration of trial medication that might reasonably influence the results of the trial (incl. QT/QTc interval prolongation)
12. Participation in another trial (including bioequivalence trial) where an investigational drug has been administered within 3 months prior to planned administration of trial medication
13. Current smoker or ex-smoker who quit smoking less than 30 days prior to screening
14. Inability to refrain from smoking on specified trial days
15. Alcohol abuse (consumption of more than 20 g per day)
16. Drug abuse or positive drug screening
17. Blood donation of more than 100 mL within 30 days prior to administration of trial medication or intended donation during the trial
18. Intention to perform excessive physical activities within one week prior to administration of trial medication or during the trial
19. Inability to comply with dietary regimen of trial site
20. Subject is assessed as unsuitable for inclusion by the investigator, for instance, because considered not able to understand and comply with study requirements, or has a condition that would not allow safe participation in the study.
21. Any relevant finding of the gynaecological examination
22. Thrombotic predisposition according to thrombophilic testing
23. Existing or history of arterial thrombotic or embolic processes, conditions which predispose to them e.g. disorders of the clotting processes, valvular heart disease and atrial fibrillation
24. Existing or history of confirmed venous thromboembolism, family history of venous thromboembolism, and other known risk factors for venous thromboembolism.
25. Relevant varicosis
26. Use of hormone-containing intrauterine device, depot injection or contraceptive implants

For study restrictions, refer to [Section 4.2.2](#).

